Other than viral vaccines for cancers of known viral origin, vaccines for prevention of cancer have not received sufficient attention. Yet, there are many non-viral antigens that are differentially expressed between normal and cancer cells, such as MUC1, that are perceived by the immune system as foreign and to which immune responses can be safely generated through vaccination. In preclinical animal models of human cancer, these vaccine-elicited immune responses have prevented cancer development or cancer progression. These studies have served as the basis for the first clinical feasibility study of the MUC1 peptide vaccine in individuals with the history of advanced adenoma who are considered at increased risk for developing colon cancer³⁴. This study showed that the vaccine consisting of 100mcg of the synthetic 100mer MUC1 peptide admixed with the TLR-3 agonist Hiltonol as adjuvant, induced anti-MUC1 IgG and long term immune memory thus confirming its immunogenicity. The study also showed that individuals with above normal numbers of circulating myeloid derived suppressor cells (MDSC) were prevented from responding to the vaccine. The randomized placebo-controlled trial described in this protocol will confirm the vaccine immunogenicity and its dependence on the MDSC and compare adenoma recurrence in vaccine responders vs. non-responders.

Colorectal Adenomas

MUC1 is overexpressed and hypoglycosylated on premalignant lesions such as adenomatous polyps, and its expression is significantly greater with higher degrees of dysplasia⁷. MUC1 is functionally important in the maintenance of the malignant phenotype. Thus, induction of an immune response against MUC1 in the setting of pre-malignancy, such as in patients with adenomatous polyps, may protect from polyp recurrence as well as from progression to cancer.

[figure not shown]

Figure1: Abnormal MUC1 is overexpressed and hypoglycosylated. Hypoglycosylated MUC1 exposes the disaccharide T antigen and the shorter monosaccharide Tn antigen attached to the protein backbone of MUC1 molecules.

Mouse model of MUC1 vaccine for colon cancer prevention

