2.4 Studies Planned in the Proposed Trial

Evaluation of anti-MUC1 antibody titer and MUC1 expression in adenomas in relation to adenoma recurrence

Anti-MUC1 IgG will be measured at w12 and w55 to measure the immune response to the vaccine in comparison to placebo, and at the time of the endpoint surveillance colonoscopy to examine the relationship between antibody titer and adenoma recurrence. In addition, sections of the qualifying advanced adenoma and of any recurrent adenomas will be obtained. Comparison of tumor associated

MUC1 antigen expression on the recurrent adenomas in relation to antibody response, and comparison among vaccine responders, non-responders, and the control group are planned.

Evaluation of anti-MUC1 antibody responses and pre-vaccination levels of circulating MDSC

Heparinized blood will be collected at week 0, 2, 10, and 12 and live PBMCs stored in DMSO and LN2 at -70 to -80°C. We plan measurements of levels of circulating MDSC in all participants. We know from the feasibility study that higher levels of MDSC were associated with lack of generation of vaccine induced antibodies. We will confirm this observation in a larger number of individuals and will evaluate MDSC levels as a variable influencing adenoma recurrence. In the placebo group, we expect to have MDSC low and MDSC high individuals in whom we can determine if adenoma recurrence rates might correlate with MDSC.

Using samples stored in the biorepository, eventually, stored PBMCs will be used to evaluate MUC1 specific T helper and CTL responses. These studies are more time intensive and expensive and funding for them will have to be obtained through other sources or other NCI grants. We do not anticipate difficulty obtaining funding for sophisticated immune assessments on this unique collection of clinical samples among participants undergoing a randomized trial of immunotherapy in a prevention setting. Within this trial, we are using T dependent antibody responses and T dependent memory responses as a surrogate marker of vaccine elicited T cells.

Placebo Response

There are several important reasons to include a placebo group. We do not know the frequency of spontaneous acquisition of antibodies to MUC1, nor do we have data on the natural history of fluctuation in antibody level over time. A control group with which to compare the antibody response and a control group with which to compare adenoma recurrence is essential.

Exclusion of Individuals with Cancer

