3.3 Vaccine and Clinical Endpoints

The response to the vaccine will be evaluated by monitoring changes in IgG anti-MUC1 antibody titer ratio; defined as t_{12}/t_0 , where t_0 is the "initial titer" measured prior to vaccination, and t_{12} is the "final titer" drawn at 12 weeks. For the primary endpoint, the titer measured 2 weeks after the 3rd vaccination, at week 12, will be compared to the baseline titer at week 0. Because IgG is more commonly induced and more likely to be detected because of the better quality of reagents, IgG levels will be the indicator of immunogenicity. A titer ratio of ≥ 2 will be considered an immune response. The use of a titer ratio permits a uniform definition for an immunologic response regardless of the baseline level of MUC1 antibody. The titer ratio at week 12 will mark the close of Part 1 of the trial. The assessment of the response to the booster vaccine will be evaluated by examining the week 55 titer to the titer at week 52, prior to receipt of the booster vaccine. Once again, a titer ratio of ≥ 2 for the T55/T52 comparison will be considered a positive immune response.

The titer ratio of 2:1 as a measure of immune response was chosen in part from the infectious disease literature where this ratio is often employed as a marker of immune response. This ratio was commonly attained (44%) in our pilot study in participants with advanced adenoma³⁴. A titer increase of ≤ 2 may also have clinical efficacy. We have no preliminary information to identify what titer ratio may be associated with a clinical endpoint. The measurement of the response to the booster vaccine and communication with the patient regarding response (week 55) will mark the close of Part 2 of the trial.

The week 156 endpoint will be adenoma recurrence. Adenoma prevention trials testing chemoprevention regimens have been performed for a variety of compounds ranging from beta carotene, calcium, folate, aspirin, DFMO, dietary modification, fiber supplementation, etc. Although there have been repeated calls for trials using other intermediate endpoints such as aberrant crypt foci, adenoma recurrence remains the mainstay in examining the efficacy of an agent in relation to colorectal cancer. The adenoma is a reproducible measure, with a reproducible, standardized nomenclature implemented by pathologists.

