13.5 Secondary Objectives, Endpoints, Analysis Plans

As discussed previously, there will be key powered secondary endpoints for this study across all 3 parts.

1) Immune response at 12 weeks (Part 1): The key secondary endpoint for Part 1 will compare the proportion of patients that have at least a 2-fold increase in the IgG ratio (week 12/week 0) between MUC1 and placebo. Based on the pilot study³⁷, we hypothesize that around 40% of vaccinated participants will demonstrate a 2 fold increase in MUC1 titer at week 12 compared to around 10% for the placebo arm. Assuming a drop-out rate of up to 10% by 1 year (presumably less by 12 weeks), retaining at least 50 evaluable participants per arm provides 94% power to detect an increase in the 12-week immune response rate from 10 to 40%, assuming a 2-sided significance level of 0.05 (nQuery Advisor 6.01).

2) Booster Response at 1 year (Part 2): The key secondary endpoint for Part 2 will assess the booster response at week 55 vs. week 52 for the vaccine as compared to placebo. Based on the pilot study, we expect 75% of week-12 responders will respond with a doubling of MUC1 antibody levels, or about 35% of the overall sample. We expect the 1-year response rate to be around 10% in the placebo group. Of the 110 randomized participants (55/arm), we expect that up to 10% will drop out by 1 year, leaving

approximately 100 participants evaluable for this analysis (50/arm). With 50 evaluable participants per arm, we would have 92% power to detect an increase in the 1-year immune response rate from 10 to 35%, assuming a 1-sided significance level of 0.05 (nQuery Advisor 6.01). We will also compare the actual IgG ratio values between the 2 treatment arms as well. If the booster vaccine shows a significant increase in the 1-year immune response as compared to placebo and a response rate that exceeds 15%, we can proceed to Part III.

3) Adenoma recurrence rate at 3 years (Part 3): Part 3 will evaluate the adenoma recurrence rate at least one year and up to 3 years. The adenoma recurrence rate at 3 years in participants with an adenoma is generally around 40-50%³³. Assuming an additional 10% drop out rate between years 1 and 3, we will have 90 participants (45/arm) evaluable for this endpoint, which will provide >80% power for the different effect sizes shown in the table below (1-sided alpha = 0.05).

# Evaluable	Effect Size (delta)	Power	1-sided alpha
90 (45/arm)	50 vs. 25%	79%	0.05
90 (45/arm)	45 vs. 20%	82%	0.05

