13.10 Ancillary Studies

We will assess the following translational endpoints for this study.

- To compare the anti-MUC1 antibody titer at the time of surveillance colonoscopy to evaluate the anti-MUC1 antibody response in relation to adenoma recurrence. Since surveillance colonoscopy is generally at 3 years after an advanced adenoma, this titer will typically be obtained at approximately week 156.
- To evaluate MUC1 expression on baseline advanced adenomas and on recurrent adenomas detected at surveillance colonoscopy. Based on current knowledge of MUC1 expression and function in tumor cells, MUC1 negative adenomas are not expected to grow as immune escape variants, but this has never been tested before and the trial will provide an appropriate setting to study this issue.
- To evaluate levels of circulating myeloid derived suppressor cells (MDSC) in the vaccinated and the placebo group and correlate with anti-MUC1 antibody levels and adenoma recurrence.
- To establish a biospecimen repository archive including live cells, plasma, and germline DNA for future immunologic and other assays, for testing not currently accommodated within the budget of this trial.

Analysis of these translational endpoints:

Laboratory measures will be correlated with participant outcome (i.e., adverse events, IgG levels, etc.) and with each other as well. Cut-points will be determined based on previously defined and accepted standards. Descriptive statistics and simple scatter plots will be generated to review the continuous biomarker data. In addition, for continuous biomarker values, the actual and % change in the level of each of the biomarkers from baseline to post-baseline time points will be explored within each arm using Wilcoxon signed rank tests, and paired sample t-tests. Comparisons between MUC1 and placebo will be performed using a two-sample t-test or Wilcoxon rank sum test, as appropriate. All categorical variables will be analyzed using chi-square tests or Fisher's exact test. For all translational endpoints, any notable statistical result will be viewed as an impetus for further study rather than as a definitive finding in and of itself.

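### The planned responder versus non-responder comparison of adenoma recurrence is unadjusted, so it mixes any vaccine effect with prognosis linked to MDSC level

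*Combined protocol and SAP*

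**What the plan says.** In Section 2 (Background, under Vaccines for Prevention) the protocol says the trial will "compare adenoma recurrence in vaccine responders vs. non-responders". The same paragraph reports from the feasibility study that "individuals with above normal numbers of circulating myeloid derived suppressor cells (MDSC) were prevented from responding to the vaccine". Section 2.3 puts this more softly, as a correlation between non-response and high MDSC.

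Section 2.4 says the investigators "will evaluate MDSC levels as a variable influencing adenoma recurrence", and it plans to look at MDSC against recurrence in the placebo group.

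Sections 1.3, 8.2 and 13.10 list two related translational items: anti-MUC1 titer at surveillance colonoscopy in relation to recurrence, and MDSC correlated with antibody level and with recurrence.

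For methods, 13.10 gives correlations, t or Wilcoxon tests for continuous measures, and this for the rest: "All categorical variables will be analyzed using chi-square tests or Fisher's exact test". It specifies no covariate adjustment and no stratification by MDSC.

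Response itself is defined in Section 3.3: "A titer ratio of ≥ 2 will be considered an immune response", with the ratio taken at week 12 relative to week 0.

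**The concern.** Responder status is not assigned by randomization. It is a trait that shows itself after vaccination, and the protocol names a pre-vaccination characteristic that it believes drives it. The protocol also suspects that this characteristic may affect recurrence. One baseline factor linked to both the grouping variable and the outcome is confounding. Taking the response early, at week 12, does not remove it.

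An unadjusted test asks whether recurrence depends on responder status. The question of interest is whether vaccine-induced immunity lowers recurrence. The two coincide only if responders and non-responders would have had the same recurrence without vaccine. If they would not, a difference in favour of responders could be taken as a signal of protection and used to justify further work, when part or all of it reflects who was able to respond.

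**Working it through.** **1. Inputs from the documents.**
- Part III evaluable: 45 per arm (13.5).
- Response, vaccine arm: "we hypothesize that around 40% of vaccinated participants will demonstrate a 2 fold increase in MUC1 titer at week 12" (13.5). 0.40 × 45 = 18 responders and 27 non-responders.
- Response, placebo arm: "compared to around 10% for the placebo arm" (13.5). 0.10 × 45 = 4.5, too few to serve as a placebo responder group.
- Background recurrence: "The adenoma recurrence rate at 3 years in participants with an adenoma is generally around 40-50" per cent (13.5). The midpoint, 45%, is used.

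**2. The plan's own figures.** None exists for the responder contrast. The nearest is Part III power for the randomized comparison, stated as 79%, 82% and 85% (one-sided 0.05). The pooled-variance formula is

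power = Φ{ [|p1 − p2| − 1.645 √(2p̄(1 − p̄)/n)] / √[(p1(1 − p1) + p2(1 − p2))/n] }.

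For 50 vs 25% and n = 45: [0.25 − 1.645 × 0.1021] / 0.0986 = 0.833, and Φ(0.833) = 79.75%. The other rows give 82.1% and 85.4%. The plan's figures reproduce.

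**3. Inputs the documents do not give (assumed).** Three settings, each giving about 40% response overall:
- A: 50% MDSC-high; response 10% in MDSC-high, 70% in MDSC-low.
- B: 50% MDSC-high; response 20% vs 60%.
- C: 30% MDSC-high; response 10% vs 53%.

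MDSC-high/low recurrence is set at 45/45, 50/40, 55/35, 60/30 and 65/25%, and depends on MDSC only. The vaccine does nothing.

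**4. Spurious gap, by arithmetic.** The gap equals (MDSC-high share of non-responders − MDSC-high share of responders) × (MDSC recurrence gap).
- A: 0.45/0.60 − 0.05/0.40 = 0.750 − 0.125 = 0.625.
- B: 0.40/0.60 − 0.10/0.40 = 0.667 − 0.250 = 0.417.
- C: 0.27/0.599 − 0.03/0.401 = 0.451 − 0.075 = 0.376.

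Worked case, A with 60/30%:
- Responders: (0.05 × 0.60 + 0.35 × 0.30)/0.40 = 33.8%.
- Non-responders: (0.45 × 0.60 + 0.15 × 0.30)/0.60 = 52.5%.
- The gap is 0.625 × 30 = 18.75 points with no vaccine effect.

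**5. False-positive rate.** Simulation of the 45 vaccinated participants, 20,000-40,000 replicates per scenario, uncorrected chi-square test, two-sided 0.05:

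| MDSC recurrence gap | A | B | C |
|---|---|---|---|
| 0 points | 5% | 5% | 5% |
| 10 points | 7% | 6% | 6% |
| 20 points | 13% | 8% | 8% |
| 30 points | 23% | 13% | 11-12% |
| 40 points | 38% | 19-20% | 17% |

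Over the nine scenarios with gaps of 20 to 40 points, chi-square reaches at least 10% in seven. Fisher's exact test, which 13.10 equally allows, does so in four.

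**6. Direction.** With the sign reversed under A (MDSC-high 40%, MDSC-low 50%), the test rejects 7.1% of the time, and only 1.0% is in the vaccine's favour.

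**7. Alternatives, same nine scenarios.** A Mantel-Haenszel responder test stratified by MDSC, and vaccine versus placebo within MDSC-low participants, both stay at about 4.3-5.3%. For the stratified responder test this holds because MDSC is the only confounder in the simulation. The within-stratum arm comparison is protected by randomization.

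**The case against.** The strongest reply is that this is half a sentence in the Background. The responder contrast is not named in the objectives, the endpoints or Section 13, and no passage assigns the chi-square test to it. The nearest listed item uses the titer at colonoscopy, which is a different exposure. Efficacy on recurrence rests on the randomized MUC1 versus placebo comparison. Section 13.10 says notable translational results are a prompt for further study and not definitive. Section 2.4 calls a control group for recurrence essential and plans to examine MDSC against recurrence in placebo participants.

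All of this is correct and limits the point to an exploratory analysis. It does not remove the point. The contrast is stated as something the trial will do, the related titer analysis carries the same confounding, and nothing links the placebo MDSC check to either. A caution about definitiveness does not correct a bias in the signal.

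The reply is also right that the size is assumption-driven: at a 10-point gap the inflation is slight.

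A reader might infer that the contrast measures prognosis and not vaccine effect, or that it always errs in the vaccine's favour. The documents support neither. It mixes prognosis with any real antibody effect, and the direction depends on an MDSC-recurrence relation that the protocol leaves open.

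**Conclusion.** The concern holds for the crude responder contrast and the related unadjusted analyses. The comparison is not protected by randomization, and the protocol itself identifies MDSC as linked to response and possibly to recurrence. If high MDSC raises recurrence, an inert vaccine can appear protective. Over the assumed settings the false-positive rate runs from nominal (no association) to 38% (a 40-point MDSC gap with a strong MDSC-response link). These figures illustrate sensitivity and do not estimate what this trial will show, because MDSC prevalence, response by MDSC and recurrence by MDSC are all assumed.

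It would be wrong to infer that the trial's efficacy conclusion on recurrence is compromised, since the Part III comparison of randomized arms does not use responder status. The weakness lies in an exploratory analysis, and it can be cured cheaply before unblinding.

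**What to change.** In 13.10, with Section 2 reworded to match:

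1. As the exploratory analysis, compare vaccine with placebo on Part III recurrence by baseline (week 0) MDSC level, using strata or an arm-by-MDSC term. Fix the MDSC cut-point before unblinding; 13.10 now refers only to accepted standards.
2. If the responder contrast is kept, adjust or stratify it by baseline MDSC and show the placebo arm's recurrence by MDSC beside it. State that it is not a randomized comparison and that unmeasured confounding may remain.

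The cost is wording and a little analysis. Section 2.4 already plans week 0 cell collection and MDSC measurement in all participants, so no new samples or visits are needed.

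The price is precision. If MDSC splits evenly, each stratum holds about 20-25 per arm. The formula above with n = 20 to 25 then gives roughly 50-64% one-sided power for the plan's 25-point effects, against 79-85% for the full comparison. Adjusting for MDSC also widens the interval for the responder contrast. The analysis therefore remains exploratory.

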2.1 Study Disease: Advanced Adenomas

Advanced adenomas (AAs) are defined as pre-neoplastic adenomatous polyps that are either: 1) ≥ 1 cm in size, 2) demonstrate villous or tubulovillous histology, or 3) have severe or high grade dysplasia. Advanced adenomas occur in about 5-10% of patients undergoing screening colonoscopy. Individuals with AAs are a high risk group. Studies show that individuals having an advanced adenoma have a 2 fold or more risk of having a recurrent AA compared to individuals with non-advanced adenomas^{38,39}, and more importantly, are at higher risk for subsequent colorectal cancer, even years later^{8,40}. Patients with AA are an appropriate group to focus on for prevention. Low levels of anti-MUC1 IgG can be detected in patients with advanced adenomas⁴¹. Most recently, we performed a pilot study of MUC1 vaccine in patients with a prior history of advanced adenoma, though not necessarily recently diagnosed advanced adenomas, and the vaccine was well tolerated with no significant toxicity³⁴.

2.2 Study Agent: MUC1 Vaccine (MUC1 peptide/Poly-ICLC)

A certified clinical grade 100-amino acid synthetic MUC1 peptide with the molecular structure of H₂N-(GVTSAPDTRPAPGSTAPPAH)₅-CONH₂, will be synthesized at the University of Pittsburgh Peptide Synthesis Facility. The adjuvant, toll like receptor (TLR) 3 agonist, Poly-ICLC (Hiltonol®), will be supplied by Oncovir Inc. (Washington, DC) in single-dose vials of 1mL solution containing 2mg poly-IC, 1.5mg poly-L-lysine, and 5mg sodium carboxymethylcellulose in 0.9% sodium chloride, adjusted to pH 7.6-7.8 with sodium hydroxide. The vaccine will consist of 100 micrograms (0.1mg) of the MUC1 100mer peptide dissolved in 50mL (0.05mL) of sterile saline, admixed with 500mcg (0.5mg) of Hiltonol® in 250mL (0.25mL), for a total injection volume of 300mL (0.3mL).

2.3 Rationale

Completed Feasibility study of MUC1 Vaccine at U. of Pittsburgh

We enrolled 40 participants who received MUC1/Poly ICLC vaccine at 0, 2, and 10 weeks and antibody titers were evaluated prior to each vaccination and at week 12, 28 and 52³⁴. In the 39 participants that received all three initial doses of vaccine, 17 (44%) had over a two-fold ratio increase at week 12, ten participants had ratios over 4.5 fold, and another 4 participants had a ratio increase from 1.4 – 2.0. The kinetics of the response were similar, with peak antibody levels generally occurring after the third injection. As expected, circulating antibody levels tended to decline over the next year with clearance of the vaccine antigen.

Response to Booster vaccine

To test for the presence of a vaccine-induced T cell memory response, participants received a booster dose of vaccine at 1 year. Of the 16 participants who responded to the initial vaccination and received the booster, 12 (75%) had a two-fold ratio increase when comparing week 54 to week 52. Three of the 4 who didn't have a two-fold elevation at week 54 had maintained high levels of antibody at week 52, hence did not manifest a 2 fold ratio increase at week 54. Overall, the results suggest that responders established a T cell memory response to the MUC1 antigen.

Adverse Events

Over 150 vaccinations were administered in the pilot study. No adverse events above grade 1 were identified, and no unanticipated adverse events were observed. Most participants developed erythema with soreness at the injection site. Some developed short lived fever and muscle aches, which respond well to analgesics such as Tylenol. We had nearly 100% compliance with the study protocol. Participants were monitored with immunofluorescent ANA titers pre vaccination and at 1 year. No participants have developed a change in ANA titer and no new autoimmune diseases were observed.

Figure 2:

[figure not shown]

Figure 2A: Ratio response in MUC1 antibody.
Figure 2B: Kinetics of response to vaccination at 0, 2, and 10 weeks (arrows under x axis) and to booster vaccine at week 52.

Evaluation of Immune Non-Responders

Lack of response to vaccination was correlated with high levels of circulating myeloid-derived suppressor cells but not to circulating T regulatory cells.

